9.4.4 Clinical Pregnancy Rate

The clinical pregnancy rate will be calculated for the fresh cycle, for each cryopreserved cycle sequentially (overall and within programmed and natural cycles separately), cumulatively for the cryopreserved cycles, and cumulatively across the fresh and cryopreserved cycles based on both the total number of subjects in the treatment group and the total number of subjects who started the respective cycle. The analyses will be conducted in a similar manner as ongoing pregnancy rate and will be applied to both the mITT and PP analysis sets. For subjects with clinical pregnancy, the type of clinical pregnancy (intrauterine or ectopic) will be tabulated.

9.4.5 Vital Pregnancy Rate

The vital pregnancy rate will be calculated and analyzed in a similar manner as ongoing pregnancy rate and will be applied to both the mITT and PP analysis sets.

9.4.6 Implantation Rate

The implantation rate will be calculated and analyzed in a similar manner as ongoing implantation rate and will be applied to both the mITT and PP analysis sets.

9.4.7 Positive βhCG Rate

The positive β hCG rate will be calculated and analyzed in a similar manner as ongoing pregnancy rate and will be applied to both the mITT and PP analysis sets.

9.4.8 Triggering of Final Follicular Maturation, Cycle Cancellation and Transfer Cancellation

The proportion of subjects with triggering of final follicular maturation will be tabulated by triggering drug (hCG, GnRH agonist) and in total. The proportion of subjects with cycle cancellation or transfer cancellation in the cycle will also be tabulated, including the reasons as described in Section 4 for the summary of subject disposition with respect to cycle and transfer cancellations. In addition, the proportion of subjects with transfer cancellation in cryopreserved cycles will be tabulated.

9.4.9 Number and Size of Follicles during Stimulation

The follicle cohort on stimulation day 5 and end-of-stimulation will be summarized by treatment on the follicle level (number of follicles 8-9 mm, 10-11 mm, 12-14 mm, 15-16 mm and \geq 17 mm) and on the subject level (total number of follicles, size of largest follicle, average follicle size, average size of three largest follicles, and number of follicles \geq 8 mm, \geq 10 mm, \geq 12 mm, \geq 15 mm and \geq 17 mm). Continuous data will be compared between treatment groups using Wilcoxon's test. Categorical data will be compared between treatment groups using the chi-square test or Fisher's exact test in case of sparse data. The analyses will be applied to both the mITT and PP analysis sets.

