7.1.9 Number and Size of Follicles during Stimulation

Transvaginal ultrasound will be performed at all visits during the controlled ovarian stimulation period to count the number of follicles and measure the size of the follicles. Each follicle will be measured in 2 dimensions, and its diameter will be calculated as the mean of the largest diameter and its perpendicular value.

The total number of follicles and number of follicles with a diameter of 8-9 mm, 10-11 mm, 12-14 mm, 15-16 mm, and ≥ 17 mm on stimulation day 5 and at end-of-stimulation will be recorded. Data will be recorded separately for the right and left ovary.

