3.2 Determination of Sample Size

The proposed sample size of 550 (FE 999049:placebo = 500:50) can adequately address both the efficacy and safety objectives of the trial:

- The cumulative ongoing pregnancy rate in the FE 999049-treated subjects aged 35-42 years is estimated to be approximately 30% according to results from clinical trials conducted in the U.S.¹ By comparison, the pregnancy rate in the placebo arm is expected not to exceed 3%, the monthly spontaneous pregnancy rate in infertile women.² Therefore, the proposed sample size of 550 (FE 999049:placebo=500:50) will provide at least 99% power for the primary efficacy comparison. Based on the estimated cumulative ongoing pregnancy rate, the cumulative live birth rate from the fresh and/or cryopreserved cycles is estimated to be approximately 27%, resulting in a power for the comparison of the cumulative live birth rate to be at least 99%.
- A key pharmacodynamic parameter in subjects aged 35-42 years is cycle cancellation due to poor follicular development, which may occur in approximately 5% of the population exposed to gonadotropins.
- The safety and tolerability of daily rFSH preparations as part of an ART treatment cycle have been well documented for the population studied in previous clinical trials.^{3,4} OHSS was reported to occur in 1.7% to 3.7% of the subjects, with moderate/severe OHSS occurring in 1.4% to 2.2% of the subjects. Other adverse events were pelvic pain, pelvic discomfort and headache, with those assessed to be related to trial treatments reported in 1.5% to 7.1% of the subjects.

Table 1 shows that the planned sample size of 500 subjects exposed to FE 999049 provides a high probability to detect a rare adverse event or safety signal occurring in 0.5% or more subjects.

Incidence rate of rare event	Chance of detecting at least 1 event
0.5%	91.8%
0.6%	95.1%
1%	99.3%

Table 1Probabilities to Detect at Least One Rare Event

Table 2 presents the margin width estimates of the 95% confidence intervals for a range of adverse event rates with the planned sample size.

Adverse event rate	Margin of error width estimate
5%	1.9%
10%	2.6%
15%	3.1%
20%	3.5%

Table 2Estimated Margin Widths of 95% Confidence Intervals

4 Subject Disposition

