9.2 Analysis and Presentation of Primary and Secondary Efficacy Endpoints

Summary tables and treatment comparisons for the primary endpoint will be presented for both the mITT and PP analysis sets. In case that the mITT and ITT analysis sets are not identical (i.e. at least one subject is randomized but not exposed) the summary tables and treatment comparisons will also be presented for the ITT analysis set. As applicable for the secondary endpoints, summary tables and treatment comparisons may be presented for the mITT and PP analysis sets.

All tabulations will be presented by treatment group. Continuous variables will be presented with number of subjects, mean, standard deviation, median, inter-quartile range, minimum, and maximum. Categorical variables will be presented with number and percentage of subjects within each specific category.

All statistical tests will be performed using a two-sided test at a 5% significance level. Treatment differences will (where appropriate) be presented with 95% confidence intervals and p-values corresponding to the statistical test of the hypothesis of 'equal effect' against the alternative of 'different effect'.

Visual displays will be produced as appropriate. All primary and secondary efficacy endpoints will be listed. Listings will only be produced for the mITT.

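### As worded, SAP 9.4.9 sends follicle-level size classes to chi-square or Fisher, which ignores clustering of follicles within women

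*SAP*

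**What the plan says.** SAP 9.4.9 describes the follicle data at two levels. It states: "The follicle cohort on stimulation day 5 and end-of-stimulation will be summarized by treatment on the follicle level", in five size classes (8-9, 10-11, 12-14, 15-16, and 17 mm or more). At the subject level it lists the total number of follicles, the largest and average sizes, and the number at or above each of five thresholds. All of these are numeric.

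Two test sentences follow: "Continuous data will be compared between treatment groups using Wilcoxon's test", and "Categorical data will be compared between treatment groups using the chi-square test or Fisher's exact test in case of sparse data". The analyses are run on both the mITT and PP sets. Protocol 9.7.3.9 gives the same plan. Neither section names the unit of analysis for the categorical test, and neither mentions correlation between follicles of the same woman.

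SAP 9.2 sets the level: "All statistical tests will be performed using a two-sided test at a 5% significance level". SAP 9.2.1 treats the secondary efficacy endpoints as supportive, without multiplicity adjustment. Protocol 7.1.9 has the number of follicles in each size class recorded for every woman, and adds: "Data will be recorded separately for the right and left ovary".

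**The concern.** Pearson chi-square and Fisher's exact test assume independent units. Follicles from one woman share her ovarian reserve and her drug exposure, so their sizes can be expected to be positively correlated. A test that counts follicles as the sample then overstates the information and rejects too often.

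The number and size of follicles is a named secondary endpoint serving the objective of characterising ovarian response. With two time points and two analysis sets, the literal rule yields up to 2 x 2 = 4 such p-values. At stake is false precision in a pharmacodynamic result. There is also a risk to reproducibility: two programmers could follow 9.4.9 in good faith and report different tests.

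**Working it through.** **1. What the categorical sentence can apply to.** Neighbouring sections use almost the same pair of test sentences, but each gives the categorical one a woman-level variable:

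- SAP 9.4.10: subjects grouped by number of oocytes.
- SAP 9.4.11: metaphase II oocytes per subject, in classes.
- SAP 9.4.12: fertilised oocytes per subject, in classes.
- SAP 9.4.14: endometrial echogenicity pattern, one value per woman per visit.
- SAP 9.4.13: embryo-level data get frequency tables, and the tests are named for per-woman variables.

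SAP 9.4.9 has a level below the woman, no woman-level categorical variable, and no separation of the kind made in 9.4.13. By elimination, the size class is the only listed item left for chi-square or Fisher.

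**2. Inputs for sizing the effect.** The plan states no figure for this analysis, so there is none to reproduce.

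- Women per arm: 500 and 50 (SAP 3.2).
- Level: two-sided 5% (SAP 9.2).
- Classes: five (SAP 9.4.9).
- Follicles per woman: not stated. Assumed 10 on active, and 10, 5, 4 or 2 on placebo.
- Within-woman correlation r: not stated. Assumed 0 to 0.3.

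**3. Simulation under no effect.** Each follicle has a latent value sqrt(r) x (woman effect) + sqrt(1 - r) x (follicle effect), both standard normal. The value is cut into five equally likely classes. The pooled 2 x 5 table is tested by Pearson chi-square on 4 degrees of freedom. Rejection rates of the nominal 5% test, from 10,000 trials per cell (Monte Carlo standard error 0.2 to 0.4 points):

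| Follicles, active v placebo | r = 0 | 0.05 | 0.1 | 0.2 | 0.3 |
|---|---|---|---|---|---|
| 10 v 10 | 5.3% | 7.3% | 9.8% | 16.7% | 22.5% |
| 10 v 5 | 5.1% | 5.8% | 7.1% | 10.1% | 12.7% |
| 10 v 4 | 5.2% | 5.6% | 6.6% | 8.2% | 11.0% |
| 10 v 2 | 5.1% | 5.2% | 5.8% | 6.1% | 6.7% |

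Smaller runs of the same model (2,000 trials per cell) spread from 6.9% to 23.2% for 10 v 10 at r = 0.05 to 0.3. For 10 v 2 they spread from 4.9% to 8.0%. The rounded ranges are therefore 7% to 23% and 5% to 8%.

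**4. Sensitivity to the correlation scale.** If the intraclass correlation (ICC) is instead defined on the class indicators, the variance inflation with m follicles per woman in both arms is 1 + (m - 1) x ICC. The true error of the five-class test is the probability that a chi-square on 4 degrees of freedom exceeds 9.488 divided by that factor.

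- m = 10, ICC 0.05: factor 1 + 9 x 0.05 = 1.45; 9.488/1.45 = 6.54; error about 16%.
- m = 10, ICC 0.3: factor 1 + 9 x 0.3 = 3.7; 9.488/3.7 = 2.56; error about 63%.

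For 10 v 2 follicles, the clustered variance is divided by the naive variance, summed over both arms. At ICC 0.3 this is (3.7/5000 + 1.3/100) / (1/5000 + 1/100) = 0.01374/0.0102 = 1.35, an error of about 13%. At ICC 0.05 the ratio is 1.06 and the error about 6%. Dirichlet-multinomial simulation agrees with these values.

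The same nominal correlation means different things on the two scales, so the rows must not be mixed. On both scales the error is upward. It shrinks when placebo women have few follicles, because those 50 women dominate the variance and few follicles each leave little clustering.

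**5. Does the remedy hold its level?** With 10 follicles per woman in both arms, Wilcoxon on each woman's count in the top class rejected 4.3% to 5.6% of the time in the latent model (2,000 trials per setting, r = 0 to 0.3). In the Dirichlet-multinomial model it rejected 4.5% to 5.2%.

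**The case against.** The strongest reply is that the plan never says follicles will be tested. The follicle-level classes are to be summarised, and the test sentences are stock wording that need not have an object in every section. SAP 9.2 presents categorical variables as numbers and percentages of subjects, so the default unit is the woman. SAP 9.4.13, the nearest parallel, names no test at embryo level. The subject-level counts at or above 8, 10, 12, 15 and 17 mm are already headed for Wilcoxon, and their differences give every size class exactly (8-9 mm is the count at or above 8 minus the count at or above 10, and so on).

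Much of this stands. A reader might infer that the plan expressly treats follicles as independent and that the reported p-values will therefore be too small. The documents do not support that: it is the consequence of applying the section literally, and a descriptive follicle table remains a possible reading. A figure such as ten follicles per woman has no source either. Equal numbers in both arms is the unfavourable assumption, since placebo women receive no FSH.

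What does not stand is that the wording is harmless. SAP 9.2 governs how categories are presented and does not name the unit for the tests in 9.4.9. The parallel with 9.4.13 shows that the SAP separates the levels when it means to, and 9.4.9 does not. If the class counts were meant as per-woman variables, they would belong in the subject-level list, which is given separately, and the chi-square sentence would have nothing to act on.

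**Conclusion.** The point holds as a defect of wording with a statistical consequence if followed literally: chi-square or Fisher on follicle-level size classes ignores within-woman clustering and gives p-values that are too small.

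The size cannot be fixed from the documents. Under the latent model, false rejection is about 7% to 23% with 10 follicles per woman in both arms, and about 5% to 8% with 10 on active and 2 on placebo. Follicle numbers, correlation and model are all assumptions. On the ICC scale the corresponding ranges are about 16% to 63% and 6% to 13%. It is tempting to quote the largest of these as the expected error, but nothing in the protocol or SAP supports choosing it.

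Nor should a reader infer any effect on the main results. Follicle number and size is supportive and lies outside the hierarchical testing in SAP 9.2.1. The sample size and the tests of cumulative ongoing pregnancy and cumulative live birth are untouched. The change should be made, but it is a clarification of a secondary analysis.

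**What to change.** In SAP 9.4.9, state that the follicle-level size-class tables are descriptive only, in line with the embryo-level tables in 9.4.13. Compare arms on each woman's count in each size class by Wilcoxon, at both time points and in both analysis sets. Either drop the chi-square/Fisher sentence from this section or restrict it to variables with one value per woman.

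One choice should be made openly. Wilcoxon on counts asks whether women in one arm have more follicles of a given size, which depends partly on total follicle number. If the share of follicles in each class is the question, use a permutation test that reassigns whole women, or a model with the woman as the cluster.

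The cost is one or two sentences. The class counts are already recorded per woman and ovary, so no new data are needed, and neither trial conduct nor the primary analysis changes. Protocol 9.7.3.9 has the same wording, so the clarification should be listed in SAP section 14.

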9.4.10 Number and Distribution of Oocytes Retrieved

The number of oocytes retrieved will be tabulated including summary statistics. Furthermore, a frequency table with subjects grouped according to number of oocytes retrieved will be prepared using these categories: <4, 4-7, 8-14, 15-19 and \geq 20 oocytes. Subjects with cycle cancellation due to poor ovarian response will be included in the <4 oocytes group. Continuous data will be compared between treatment groups using Wilcoxon's test. Categorical data will be compared between treatment groups using the chi-square test or Fisher's exact test in case of sparse data. The analyses will be applied to both the mITT and PP analysis sets.

9.4.11 Number of Metaphase II Oocytes

Oocytes undergoing ICSI will have their maturity stage assessed prior to insemination. Maturity stage will be categorized as germinal vesicle, metaphase I, metaphase II, degenerated or other. The assessment of maturity stage will be tabulated on the oocyte level, i.e. the denominator will be the number of oocytes with assessment of maturity stage.

Analyses of MII oocytes will be restricted to subjects where all inseminated oocytes are inseminated using ICSI.

The number of MII oocytes per subject will be tabulated including both summary statistics and a frequency table using the categories ≤ 6 , 6-12, ≥ 13 MII oocytes. Furthermore, the percentage of MII oocytes to oocytes retrieved for subjects where all oocytes are inseminated using ICSI will be tabulated. Continuous data will be compared between treatment groups using Wilcoxon's test.

Categorical data will be compared between treatment groups using the chi-square test or Fisher's exact test in case of sparse data. The analyses will be applied to both the mITT and PP analysis sets.

9.4.12 Number of Fertilized Oocytes and Fertilization Rate

The number of pronuclei will be counted at 19h (\pm 2h) after insemination and recorded as 0, 1, 2 or >2 (or damaged). An oocyte is defined as fertilized if it is scored as 2PN at 19h (\pm 2h). The assessment of pronuclei will be tabulated on the oocyte level, i.e. the denominator will be the number of oocytes retrieved.

The number of fertilized oocytes per subject will be tabulated including both summary statistics and a frequency table using the categories <3, 3-5, 6-10, 11-15 and \geq 16 fertilised oocytes. Furthermore, for subjects with oocytes retrieved, the rate of fertilized oocytes to oocytes retrieved (and also the rate of fertilized oocytes to metaphase II oocytes for those inseminated using ICSI) will be tabulated overall and by method of insemination. Continuous data will be compared between treatment groups using Wilcoxon's test as applicable. Categorical data will be compared between treatment groups using the chi-square test or Fisher's exact test in case of sparse data. The analyses will be applied to both the mITT and PP analysis sets.

9.4.13 Number and Quality of Blastocysts on Day 5

The evaluation on day 5 after oocyte retrieval will consist of assessment of embryo stage and classification of blastocysts according to blastocyst expansion and hatching status (1-6), blastocyst inner cell mass grading and trophectoderm grading (for those embryos with blastocyst expansion and hatching status 3-6). Furthermore, the destiny of the embryo will be recorded.

Embryo stage is classified as blastocyst, morula, degenerated or cleavage stage. For embryos still at the cleavage stage the number of blastomeres will be recorded.

Destiny at day 5 is either transferred, cryopreserved, out of trial or continue to day 6 after oocyte retrieval.

In the event of continued culture, blastocyst grading will be recorded on day 6 after oocyte retrieval.

Based on the blastocyst expansion and hatching status, blastocyst inner cell mass grading and trophectoderm grading, the blastocyst will be classified as a good-quality blastocyst if the grade is 3BB or above as illustrated in Figure 5.

3AA	4AA	5AA	6AA
3AB	4AB	5AB	6AB
3AC	4AC	5AC	6AC
3BA	4BA	5BA	6BA
3BB	4BB	5BB	6BB

Ferring Pharmaceuticals

CONFIDENTIAL

4BC	5BC	6BC
4CA	5CA	6CA
4CB	5CB	6CB
4CC	5CC	6CC

Figure 5Good-quality Blastocysts

The embryos on day 5 and day 6 after oocyte retrieval will be summarised on both the embryo level and on the subject level.

Embryo Level

At the embryo level all embryos evaluated will be included in the tables when reporting embryo stage and destiny of the embryo. Tables will be prepared for overall and by method of insemination (IVF or ICSI). Frequency tables will be produced for the embryo stage, destiny at day 5, blastocyst expansion and hatching status, blastocyst inner cell mass grading and trophectoderm grading.

Subject Level

At the subject level the following variables on day 5, day 6 and cumulatively will be derived for all subjects:

- Number of blastocysts after oocyte retrieval
- Number of good-quality blastocysts
- Rate of blastocysts to oocytes retrieved, defined as the ratio of blastocysts to number of oocytes retrieved
- Rate of good-quality blastocysts to oocytes retrieved, defined as the ratio of good-quality blastocysts to number of oocytes retrieved

The cumulative day 5 and day 6 assessment takes the last available quality assessment value on the two days for the blastocyst. These derived variables will be summarised and compared between treatment groups using the Wilcoxon's test. Tables will be produced for all subjects, for subjects with at least 1 oocyte retrieved, and by insemination method (IVF or ICSI).

Further, at the subject level the following will be derived for all subjects:

- At least one blastocyst available on day 5, day 6 and cumulatively
- At least one good-quality blastocyst available on day 5, day 6 and cumulatively
- Number of blastocysts transferred, total and by fresh and cryopreserved transfers,
- Number of blastocysts cryopreserved

These derived variables will be reported in frequency tables. The availability of blastocysts will be compared between treatment groups using the chi-square test or Fisher's exact test in case of sparse

data. The total numbers if blastocysts transferred and cryopreserved will be compared the Wilcoxon test for ordinal. Tables will be produced for all subjects, for subjects with at least 1 oocyte retrieved, and by insemination method (IVF or ICSI).

For subjects where all inseminated oocytes are inseminated using ICSI the following will be derived for each subject:

- Number of blastocysts on day 5, day 6 and cumulatively after oocyte retrieval relative to the number of MII oocytes
- Number of good-quality blastocysts on day 5, day 6 and cumulatively relative to the number of MII oocytes

These derived variables will be summarised and compared between treatment groups. The overall comparisons will be based on the Wilcoxon's test.

The analyses will be applied to both the mITT and PP analysis sets.

9.4.14 Endometrial Thickness and Echogenicity Pattern

Endometrial thickness on stimulation day 5 and at end-of-stimulation will be tabulated including summary statistics. Endometrial echogenicity pattern on stimulation day 5 and at end-of-stimulation will be tabulated. Continuous data will be compared between treatment groups using Wilcoxon's test. Categorical data will be compared between treatment groups using the chi-square test or Fisher's exact test in case of sparse data. The analyses will be applied to both the mITT and PP analysis sets.

9.4.15 Oocyte Utilization Rate and Oocyte Efficiency Index

The oocyte utilization rate (number of blastocysts transferred or cryopreserved divided by the number of oocytes retrieved) will be analyzed in a similar manner as ongoing implantation rate and will be applied to both the mITT and PP analysis sets.

The oocyte efficiency index (cumulative number of ongoing pregnancies per oocyte retrieved) will be analyzed in a similar manner as ongoing implantation rate and will be applied to both the mITT and PP analysis sets.

